9.4 Clinical Laboratory Evaluations

All routine laboratory samples will be analyzed by a central laboratory, which will provide a procedures manual and supplies. Lab reports will be reviewed, signed and dated by the Study Physician. If a value is outside of the laboratory's normal range, the clinician will indicate if it is clinically significant or not. If clinically significant, lab tests may need to be repeated and follow up with the participant's PCP should occur.

10.0 BIOMARKER STUDIES

10.1 CSF

All CSF samples will be collected in the morning before breakfast and after an overnight fast. Participants who are taking anticoagulants, warfarin (Coumadin) and dabigatran (Pradaxa) should not be screened for this trial, as these are prohibited medications. Based on clinician judgment and depending on the clinical indication, it may be suitable to discontinue participants from their anti-platelet agent (e.g., aspirin, Plavix, NSAIDs) for 5-7 days prior to lumbar puncture and until at least 24 hours after lumbar puncture. It is not required that participants be discontinued from their anti-platelet agent in order to screen and enroll in the study.

A minimal total volume of CSF (25 ml) will be required for this study. To clear any blood from minor trauma associated with needle insertion, the first 1-2 mL of CSF are discarded (or more if needed). Collected CSF is aliquoted into sterile microtubes. Approximately 2ml of CSF or volume per local laboratory requirements will be sent at ambient temperature to the CRU laboratory for protein, glucose and cell count. The remaining CSF will be immediately frozen upright on dry ice for at least 20 minutes then stored at -70 until analysis.

CSF samples will be used to measure levels of insulin, A β 42, A β 40, total tau, and phospho-tau181. Assays will be performed by the Wake Forest ADRC Biomarker Service. CSF samples will also be frozen and stored for future analysis of putative biomarkers.

10.2 Blood Collection at Lumbar Puncture Visits

All samples will be collected in the morning before breakfast and after a minimum 8-hour overnight fast. Blood samples will be collected before CSF collection, which would be processed for fasting plasma insulin, glucose, A β 42, and A β 40. Additional blood for plasma and serum will be processed and banked.

10.3 Genetic Samples, Storage and Future Use

DNA will be extracted from participant blood samples and will be analyzed for ApoE genotyping. ApoE genotyping will be used as a weighting factor for the minimization strategy during randomization. This will allow secondary analyses of data on the impact of the ApoE genotype on putative biomarkers of AD, clinical outcome measures, and adverse events. Participants will be asked to consent to optional DNA banking for future research studies. ApoE genotyping will be performed by [name] under the auspices of the ADRC Biomarker service using established protocols.

11.0 STATISTICAL PLAN

Statistical analyses will be conducted by the ADRC Biostatistics Core. To address the Primary Aim, CSF insulin values will be subjected to a repeated measures analysis of variance with treatment (saline vs. placebo) as the repeated measure, with age and baseline MMSE as covariates. Secondary analyses will examine the effect of diagnostic status (cognitively normal vs. MCI) and APOE genotype. Secondary analyses will also examine treatment-related differences for other CSF and plasma biomarkers, and for memory scores.

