3.2 Procedures

Participants were randomized to receive 10 International Units INI bid for a total daily dose of 20 International Units INI (n=36), 20 International Units INI bid for a total dose of 40 International Units (n=38) or placebo (saline bid, n=30) for 4 months. Participants were stratified by APOE- ϵ 4 carriage. Saline or insulin (Novolin R, Novo) was administered after breakfast and dinner with ViaNaseTM, an intranasal delivery system (Craft, Baker et al. 2012). Parallel versions of the cognitive protocol were administered at baseline, and months 2 and 4 of treatment. Co-primary outcome measures were delayed story recall and the DSRS which had previously demonstrated beneficial effects of insulin (Reger, Watson et al. 2008). Secondary measures included the AD Assessment Scale for Cognition (ADAS-Cog) (Reger, Watson et al. 2008), a test comprised of measures of memory, orientation, and language, with higher scores reflecting impairment ranging from 0 (best) to 70 (worst), and the ADCS-Activities of Daily Living scale (ADCS-ADL) (Galasko, Bennett et al. 1997). Baseline and post-treatment fasting CSF was analyzed for A β 42 and tau with multi-parameter bead-based immunoassay INNO-BIA AlzBio3 (Innogenetics NV). Resting PET images were obtained using a GE Advance PET scanner (GE Medical Systems, Milwaukee, WI) using a previously described protocol (Baker, Cross et al. 2011).

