5.0 STUDY OVERVIEW

The study will consist of a single site, randomized, double-blind trial comparing the acute effects of INI (20 International Units) or placebo delivered with the ViaNase device on CSF insulin levels, AD biomarkers and memory. At study entry, participants will be randomized to receive either an acute dose of insulin or of placebo first, and the other substance on a second visit. Participants who are cognitively normal or who have aMCI (n=30) will be enrolled. The primary outcome measure will consist of CSF insulin levels. Secondary measures will include a memory test and CSF biomarker levels.

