7.2 Baseline (Visit 2)

Results from all screening procedures must be reviewed and all inclusion/exclusion criteria must be met prior to proceeding to baseline. For participants whose screening visit was waived because they had received ADRC evaluations within the past 12-months will sign an informed consent form and HIPAA Authorization prior to administration of any study-related procedures.

According to the randomization schedule, the participant will receive a dose of 20 International Units insulin or placebo administered with the ViaNase device. They will then begin preparations for the lumbar puncture. After preparation, the immediate recall section of the AVLT will be administered. Blood for plasma biomarkers will then be collected immediately before and after participants undergo the lumbar puncture. Fasting plasma insulin, glucose, A β 40 and A β 42 will be measured. Additional plasma and serum will be collected and banked.

Lumbar puncture will then be performed in the morning after a minimum 8-hour overnight fast. CSF samples will be used to measure levels of insulin, A β 42, A β 40, total tau, and phospho-tau181. Additionally, CSF sample will be banked for future exploratory analysis. CSF will be collected and immediately frozen upright on dry ice. Site staff will call the participant within 24 hours from the lumbar puncture procedure to inquire about the participant's well-being and possible adverse events. Following the lumbar puncture, the delayed recall section of the AVLT will be administered. Participants will then receive a snack and instructions about post-lumbar puncture care.

7.3 Visit 3

Visit 3 will be scheduled within 2 to 6 weeks following Visit 1. Vital signs and weight will be obtained, a nasal examination will be conducted, adverse events and concurrent medications will be recorded. Procedures will follow the schedule outlined for Visit 1, except that the alternate compound (either saline or 20 International Units insulin) will be administered.

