11.1 Power Analyses

As this study is designed as a proof of concept study to determine whether the ViaNAsE device is able to deliver insulin to the CNS as evidenced by increased CSF insulin levels following insulin administration relative to saline placebo, power calculations have not been conducted. However, the proposed sample size is larger than two previous studies (Born et al. 2002; Fishel et al. that showed that administering insulin increased CSF insulin levels.

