14.2 Placebo (Sterile Saline)

The placebo will consist of sterile saline.

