14.3 Randomization

Eligible participants will be randomized on a 1:1 schedule to receive either insulin or saline first.

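### The primary CSF insulin model for this two-order crossover has no period term, and its treatment factor is labelled with saline and placebo instead of insulin and placebo

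*Combined protocol and SAP*

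**What the plan says.** The design is a two-visit, two-order crossover. Section 5.0 states that "participants will be randomized to receive either an acute dose of insulin or of placebo first, and the other substance on a second visit". Section 14.3 gives the allocation: "Eligible participants will be randomized on a 1:1 schedule to receive either insulin or saline first". Section 7.3 repeats the dosing-visit procedures at Visit 3, "except that the alternate compound (either saline or 20 International Units insulin) will be administered". Section 7.0 has the primary and secondary outcomes measured at both study visits.

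Section 11.0 is the whole analysis plan. For the primary aim it specifies a "repeated measures analysis of variance with treatment (saline vs. placebo) as the repeated measure, with age and baseline MMSE as covariates". No section mentions a period, visit, order or sequence term. Section 14.2 says "The placebo will consist of sterile saline", so the two factor levels named in Section 11.0 are the same substance. Section 11.1 shows what is meant: "increased CSF insulin levels following insulin administration relative to saline placebo".

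For the secondary outcomes, Section 11.0 says only this: "Secondary analyses will also examine treatment-related differences for other CSF and plasma biomarkers, and for memory scores". It names no model for them.

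**The concern.** The order of treatments is randomised, but the model makes no use of it. If CSF insulin drifts between the two dosing visits for any reason other than treatment, the drift enters the insulin-minus-placebo difference with opposite signs in the two orders. With equal orders it cancels from the mean and inflates the residual, so the test becomes conservative. With unequal orders, part of it stays in the estimate, in either direction.

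This contrast is the trial's only primary result, and Section 4.0 calls the information essential to designing a Phase III trial. With 30 participants and no power calculation (Section 11.1), the plan states no reserve of precision.

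The same question is open for the memory endpoint, where it is more pressing: practice on a list-learning test given twice is an obvious source of a visit effect. Section 3.2 says of the earlier study that "Parallel versions of the cognitive protocol were administered at baseline, and months 2 and 4 of treatment". This protocol mentions no parallel versions for the AVLT.

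**Working it through.** **Inputs from the documents.** 30 participants (Section 5.1), two dosing visits each, 1:1 allocation to order (Section 14.3), and the Section 11.0 model. The plan gives no power, effect size, SD, alpha or dropout figure, so there is nothing to reproduce.

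**Assumptions.** Two-sided 5% test. The paired difference d (insulin minus placebo) has residual SD 1, so everything is in units of that SD. The Visit 2-to-3 shift p is 0, 0.25, 0.5 or 1.0. The true effect is mainly τ = 0.53, close to the effect that gives 80% power with 30 pairs (0.529). Order splits are 15/15, 14/13, 16/11 and 10/20; those with 27 participants suppose some missed second visits.

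**Set-up.** Let n1 be the number insulin-first, n2 the number saline-first, and n = n1 + n2. Then d = τ − p + e for insulin-first and d = τ + p + e for saline-first.

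*Without period* (a one-sample t-test on d):
- bias = p(n2 − n1)/n
- expected variance of d = 1 + 4p²·n1·n2/[n(n − 1)]
- half-width = t(n − 1)·s/√n, where s² is that variance

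*With period:*
- estimate = mean of the two order means, with no bias from p
- SE = ½√(1/n1 + 1/n2), on n − 2 degrees of freedom

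**Equal orders, 15/15.** The variance is 1 + p²·30/29, so the SE grows by √(1 + p²·30/29) = 1.03, 1.12 and 1.43 for p = 0.25, 0.5 and 1.0. Allowing for the one degree of freedom, the interval compares as follows. Power and type I error are from 100,000 simulations per case.

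| p | Half-width without period | Half-width with period | Wider by | Power without / with (τ = 0.53) | Type I error without |
|---|---|---|---|---|---|
| 0 | 0.373 | 0.374 | – | 80% / 80% | 5% |
| 0.25 | 0.385 | 0.374 | 3% | 78% / 80% | 4% |
| 0.5 | 0.419 | 0.374 | 12% | 73% / 80% | 3% |
| 1.0 | 0.533 | 0.374 | 42% | 50% / 80% | 0.6% |

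With τ = 0.8, power at p = 0.5 is 98% without period and 99% with it.

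**14/13 completers, τ = 0.53.** Power without period is 72%, 64% and 37% for p = 0.25, 0.5 and 1.0, against 75% with it.

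**16/11 either way round, τ = 0.53.** Bias = p × 5/27 = 0.185p, downward or upward.
- p = 0.5: bias 0.09, so the estimate centres on 0.44 or 0.62; power is 50% or 82%, against 74% with period.
- p = 1.0: bias 0.185, so the estimate centres on 0.34 or 0.71 (rounded); power is 15% or 78%, against 74%.
- Type I error stays at about 5% or below.

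**10/20, p = 0.5.** Bias = 0.5 × 10/30 = 0.17, and type I error is about 10% without period. Inflation on that scale needs an imbalance this marked.

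**Do the planned covariates help?** No. With two between-person covariates in both models (8,000 simulations per case, 15/15), power was 71.7% without period against 79.0% with it at p = 0.5, and 50.1% against 79.8% at p = 1.0.

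**The case against.** The strongest reply is that order is randomised, so the treatment-only analysis is unbiased on average over the allocation. With simple randomisation of 30 people, mean bias is zero and type I error is about 5% at every shift tried. The bias above is therefore conditional on the split that occurs, or would need dropout related to order. A 10/20 or worse split has probability about 0.10 even under coin-tossing, and blocking, or the minimisation mentioned in Section 10.3, would normally make it rarer. The two dosing visits follow the same procedures (same device, morning sampling, overnight fast), and nothing in the documents shows that CSF insulin shifts between them. A shift of 1 SD of the paired difference equals about √2 = 1.4 within-visit SDs, which is large. If the treatment effect is large too, little power is lost.

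All of this is correct, and it limits the point to precision and to sensitivity to the realised split. The planned test is not invalid. But the trial will have one split. Under simple randomisation, 12/18 or worse has probability 0.36, and the need for a second lumbar puncture could unbalance completers. The loss of precision arises even at 15/15. Adding period only after seeing the data would be a post hoc choice.

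The label is only a drafting error, and silence on AVLT forms does not show that one form is used twice.

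**Conclusion.** The concern holds and should be fixed. The primary model leaves out the one within-person factor, besides treatment, that the design randomises across, and its covariates cannot stand in for it. With equal orders the consequence is a wider interval and a conservative test: negligible at a shift of 0.25 SD, moderate at 0.5 and severe at 1.0. With unequal orders the estimate also moves by p times the difference in order counts divided by n. These sizes rest on an assumed two-sided 5% test, shifts expressed in SDs of the paired difference, and a true effect of 0.53 SD. The documents neither support nor rule out a shift in CSF insulin. The case for change is that protection is almost free. The factor label needs correcting but leaves the hypothesis in no doubt.

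**What to change.** Replace the primary-analysis sentence in Section 11.0 with:

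> CSF insulin will be analysed with a linear mixed model with fixed effects for treatment (insulin vs. saline placebo) and period (Visit 2, Visit 3), age and baseline MMSE as covariates, and a random participant effect, including all available visits. The primary result is the insulin-minus-placebo difference with its 95% CI.

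The essential changes are the period term and the corrected label; adding period to the existing repeated-measures ANOVA would also meet the point. A sequence term may be added but is not needed for the within-person contrast. State the same model for the AVLT and the CSF ratios, and say whether parallel AVLT forms will be used.

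The cost is one sentence and one degree of freedom, with no new data. If there is no period effect, the term costs about 0.1 point of power at 15/15 and about 1.6 points at 16/11 (75.5% to 73.9%). The change does not resolve carryover, which has to be considered separately.

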1.1 Primary Aim

To test the hypothesis that CSF insulin levels will increase 30 minutes after receiving a 20 International Units dose of insulin delivered with the ViaNase or device, compared to levels achieved 30 minutes after placebo

1.1.1 Secondary Aim 1

1. To test the hypothesis that memory performance measured with a list learning test (Auditory Verbal Learning Test) will be enhanced after insulin administration relative to placebo

1.1.2 Secondary Aim 2

1. To test the hypothesis that the CSF A β 42/40 and the CSF A β 42/tau ratios will increase after insulin administration relative to placebo

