3.4 Statistical Analyses

For the intent-to-treat (ITT) sample, co-primary (delayed story recall and DSRS) and secondary (ADAS-Cog and ADAS-ADL) scores were log transformed. Scores were first subjected to mixed model repeated ANCOVA including all treatment groups (placebo, low dose insulin or high dose insulin) as the between subjects factor, and time (baseline, month 2, month 4) as the repeated factor using the SAS v9.2 General Linear Models procedure. After a significant ($p<0.05$) time by treatment group interaction reflecting a different pattern of change, each of the two insulin groups was compared separately with the placebo group using repeated measures ANCOVAs. Effect sizes (Cohen's f^2) were calculated for all significant effects. Age was included as a covariate in all analyses. Diagnosis (aMCI or AD), gender, APOE- ϵ 4 carriage status (yes or no), baseline 3MSE score, and years of education were also included as covariates. Non-significant covariates were dropped from the model. Significant relationships with covariates were explored with Pearson correlation (continuous variables) or follow-up ANOVAs (class variables). Missing values were treated with multiple imputation (Rubin 1987). For exploratory CSF biomarker analyses, because only a subset of participants elected to undergo LP and no differences were observed between the two insulin dose arms, the groups were combined into a single insulin-treated group to maximize power. Biomarkers were analyzed with the repeated ANCOVA strategy described above and, due to the small sample size, exploratory Spearman correlations were conducted to examine relationships among changes in biomarkers and outcome measures. Only study completers underwent post-treatment FDG-PET. Pre and post treatment scans were co-registered within subject and anatomically standardized to Talairach and Tournoux stereotactic coordinates (Talairach and Tournoux 1988, Minoshima, Koeppe et al. 1994). Pixel intensity was normalized to pontine values (Minoshima, Frey et al. 1995). Interval regional CMRglc changes within groups were assessed using voxel-wise one-sample t statistics (pre-/post-treatment pair) and probability integral conversion to z scores (Worsley, Evans et al. 1992). Interval changes in regional CMRglc were then compared between 1) low insulin vs. placebo groups, and 2) high insulin vs. placebo groups. Based on the number of voxels and smoothness of the statistical map, a Type I error rate was controlled at 0.05 to account for multiple comparisons (Worsley, Evans et al. 1992). The resulting statistical maps were visualized in three-dimensional stereotactic surface projections.

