5.1 Study Population

A total of 30 adults who are cognitively normal or diagnosed with aMCI will be enrolled in this trial. We expect to enroll approximately 50% of participants from each group. To determine eligibility, all participants will undergo cognitive assessment, physical and neurological examination, ECG, clinical/safety laboratory assessment, and interviews of the participant and study partner conducted by the investigators and staff of the Clinical Core of the Wake Forest Alzheimer's Disease Research Center (ADRC).

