5.3 Inclusion Criteria

The following inclusion criteria* will be used:

1. Age 55 to 85 (inclusive)
2. Fluent in English
3. Cognitively normal or diagnosis of aMCI by criteria described above
4. MMSE \geq 24 at screening. Approval for exceptions can be requested to the Project Director for minority or low education participants
5. CDR 0-0.5 (inclusive) at screening
6. Stable medical condition for 3 months prior to screening visit
7. Stable medications for 4 weeks prior to the screening and study visits
8. Clinical laboratory values must be within normal limits or, if abnormal, must be judged to be clinically insignificant by the study physician

*Exceptions to these criteria may be considered on a case-by-case basis at the discretion of the Project Director and study physician, and must be approved in advance by the IRB.

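### Does leaving open how age and MMSE enter the repeated-measures ANOVA put the primary test of CSF insulin at risk?

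*Combined protocol and SAP*

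**What the plan says.** Section 11.0 is the only description of the primary model. It specifies a repeated measures analysis of variance on CSF insulin, with treatment "as the repeated measure, with age and baseline MMSE as covariates". It gives no model equation, software procedure or centring rule, and no covariate values at which treatment is to be tested. It leaves diagnostic status and APOE genotype to secondary analyses and assigns the work to the ADRC Biostatistics Core.

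The target is stated elsewhere. Section 1.1 asks whether CSF insulin rises after insulin, "compared to levels achieved 30 minutes after placebo". Sections 4.3 and 11.1 describe the same comparison.

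The design is a two-period crossover. Section 14.3 has participants "randomized on a 1:1 schedule to receive either insulin or saline first", and section 5.0 gives each of them the other substance at a second visit. Section 5.1 sets the size at 30. Section 11.1 states that "power calculations have not been conducted". Section 5.3 admits ages 55 to 85 and requires an MMSE of at least 24, with exceptions possible.

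**The concern.** Age and baseline MMSE take the same value at both of a participant's treatment visits, so the way they enter the model decides what the treatment test means. As main effects they drop out of the within-person comparison. In the classical general linear model form of repeated measures, covariates are crossed with the within-person factor. The line labelled treatment is then the insulin-minus-placebo difference at covariate values of zero, unless the covariates are centred. Age 0 and MMSE 0 lie far outside the eligible range, so that line does not estimate the Primary Aim.

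The crossed form is not far-fetched. Covariates that are constant within a person can alter a complete-pairs treatment contrast only if they are crossed with treatment. Section 3.4 also shows that the first preliminary study used repeated ANCOVA with time "as the repeated factor using the SAS v9.2 General Linear Models procedure". If such an uncentred line were reported as the primary result, a device that delivers insulin to the CSF would usually appear not to, in a study meant to inform Phase III.

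**Working it through.** The plan states no power, effect size, variance or alpha for this trial, so there is no figure of its own to reproduce. Everything below is conditional on assumptions.

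**Inputs**
- n = 30 within-person differences (section 5.1), with no missing second visits.
- Two-sided alpha of 0.05 (assumed).
- Paired effect d of 0.53 SD of the difference (assumed). This is the effect at which 30 pairs give about 80% power.
- Covariates, set A: age 70.95 (SD 7.1) and MMSE 24.8 (SD 2.7), from the baseline table in section 4.0 (Preliminary Study 2). That trial admitted MMSE above 19.
- Covariates, set B: age 70 (SD 7.1) and MMSE 28 (SD 2.0), assumed so as to fit the present criterion.

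Set A's MMSE figures cannot arise on a 24 to 30 range. With mean 24.8 the largest possible SD is √[(24.8 − 24) × (30 − 24.8)] = √4.16 = 2.04. Set A is therefore only a guide.

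**Step 1: reduce to differences.** With two measurements per person, the within-person test is a regression on D = insulin minus placebo.
- Main effects only: D = b0 + e. The covariates cancel, leaving the paired test.
- Crossed: D = b0 + b1·age + b2·MMSE + e. If age and MMSE are centred, b0 is the average difference. If not, it is the difference at age 0 and MMSE 0.

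**Step 2: standard error of b0, uncentred relative to centred.** For uncorrelated covariates and large n, the ratio is √[1 + (mean age / SD age)² + (mean MMSE / SD MMSE)²].
- Set A: √(1 + 9.99² + 9.19²) = 13.6. With an age–MMSE correlation of −0.5 it is 19.2, and with +0.3 it is 12.0.
- Set B, multiplying the two squared terms by the small-sample factor n/(n − 1) = 30/29: √[1 + (30/29)(9.86² + 14²)] = 17.4.
- Over wider assumptions (age SD 6 to 15, MMSE SD 1.3 to 3, correlation −0.5 to 0.5), about 9 to 35.

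**Step 3: power when the effect does not vary with age or MMSE.** The noncentrality is d√n = 0.53 × √30 = 2.90.
- Plain paired test, 29 df: 80.1%.
- Crossed and centred, 27 df: 79.9%.
- Crossed and uncentred, set B: 2.90 / 17.4 = 0.17, giving 5.3%.

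Across the distributions tried and effects of 0.53 to 1.5 SD, uncentred power stays between about 5% and 9%. Simulation agrees.

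**Step 4: when the effect does vary.** The 5% to 9% range, and a false-positive rate of 5%, hold only if the treatment effect is constant over age and MMSE. With set A and an average effect of zero, an age slope of 0.05 SD per year puts b0 at −0.05 × 70.95 = −3.5 SD. Simulated uncentred rejection rates are:

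| Average effect | Age slope (SD/year) | MMSE slope (SD/point) | Uncentred rejection |
|---|---|---|---|
| 0 | 0.03 | 0 | 12–13% |
| 0 | 0.05 | 0 | 25–27% |
| 0 | 0.05 | 0.1 | 59–60% |
| 0.53 SD | −0.03 | 0 | 17% |
| 0.53 SD | −0.05 | 0 | 34% |

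The centred test rejects 5% to 7% of the time in the three zero-effect rows. The uncentred line can therefore mislead in either direction.

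**Step 5: the harmless reading, checked by fitting.** On one simulated data set, the paired test and a mixed model with age and MMSE as main effects both gave 0.882 (SE 0.193). Crossing the covariates uncentred on the same data gave −1.18 (SE 4.34).

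**The case for a change.** The strongest case for a change is that this is the only primary test, that no passage excludes the crossed and uncentred form, and that two or three sentences would settle the matter before unblinding at almost no cost. Leaving the model open also allows a choice after the data are seen, and the two forms can give very different answers: in one illustrative data set p was 0.008 centred and 0.28 uncentred. The arithmetic is sound, and a one-line note would do no harm.

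It does not show a fault in what the plan prescribes. Harm needs three things together: covariates crossed with treatment, no centring, and the resulting line reported as the treatment effect. The documents state none of them. Section 11.0 treats age and MMSE simply as covariates and places the participant factors whose effect it wants to examine, diagnosis and APOE, among the secondary analyses. That fits adjustment better than interaction, although this is an inference from the text. A contrast at age 0 contradicts section 1.1, and a standard error more than ten times that of the simple paired comparison would be conspicuous to the Biostatistics Core.

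Section 3.4 adds little. It describes a parallel-group trial whose key test was a time-by-group interaction, which is not exposed to this problem. It also reports dropping non-significant covariates, a practice that would tend to remove idle crossed terms.

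**Conclusion.** The omission is real, but it does not call for a change. The stated aim fixes the quantity to be tested, the average within-person insulin-minus-placebo difference. Main effects and centred crossed terms both deliver it: the first reproduces the paired test in complete pairs, and the second costs two degrees of freedom, or 0.2 percentage points of power at 0.53 SD. Only an analysis that the plan does not describe, and that would contradict its own aim, produces the 9- to 35-fold standard error and power near 5%.

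Those figures rest on assumed effect sizes, alpha and covariate distributions, and the power range also needs an effect that does not vary with age or MMSE. The judgement that no change follows rests on the analysts testing the contrast in section 1.1. Writing that down would record what the plan already implies and would not correct a rule in it.
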